6.2.3 Criteria for LDK378 dose modifications

An LDK378 dose reduction will follow the guidelines described in [Table 6-2](#). For each patient, a maximum of 3 dose modifications is allowed after which the patient must be discontinued from treatment with LDK378. Once the dose of LDK378 has been reduced, it cannot be re-escalated. If a patient continues treatment with LDK378 after RECIST-defined PD as determined by the investigator, the criteria for dose modification will also apply.

Table 6-2 Dose reduction steps for LDK378

LDK378 dose levels	Dose* and schedule
Starting dose level	750 qd continuously
Dose level – 1	600 qd continuously
Dose level – 2	450 qd continuously
Dose level – 3	300 qd continuously **

*Dose reduction should be based on the worst preceding toxicity
**Dose reduction below 300 mg/day is not allowed. If a dose reduction below 300 mg/day is required, the patient should be permanently discontinued from LDK378

Guidelines for dose modification and dose interruption of LDK378 are described in [Table 6-3](#).

Table 6-3 Criteria for interruption and re-initiation of LDK378 treatment

Worst toxicity (CTCAE 4.03 Grade)*	Dose Modifications for LDK378
HEMATOLOGICAL	
Neutropenia (ANC)	
Grade 1 (ANC < LLN - $1.5 \times 10^9/L$)	Maintain dose level
Grade 2 (ANC < 1.5 and $\geq 1.0 \times 10^9/L$)	
Grade 3 (ANC < 1.0 and $\geq 0.5 \times 10^9/L$)	
Grade 4 (ANC < $0.5 \times 10^9/L$)	Omit dose until resolved to \leq Grade 2, then: If resolved in ≤ 7 days, then maintain dose level If resolved in > 7 days, then $\downarrow 1$ dose level
Febrile neutropenia (ANC < $1.0 \times 10^9/L$, with a single temperature of $\geq 38.3^{\circ}C$ or a sustained temperature of $\geq 38^{\circ}C$ for more than one hour)	Omit dose until clinically resolved and neutropenia \leq Grade 2, then $\downarrow 1$ dose level
Thrombocytopenia	
Grade 1 (PLT < LLN - $75 \times 10^9/L$)	Maintain dose level
Grade 2 (PLT < 75 and $\geq 50 \times 10^9/L$)	
Grade 3 (PLT < 50 and $\geq 25 \times 10^9/L$)	Omit dose until resolved to \leq Grade 2, then: If resolved in ≤ 7 days, then maintain dose level If resolved in > 7 days, then $\downarrow 1$ dose level
Grade 4 (PLT < $25 \times 10^9/L$)	Omit dose until resolved to \leq Grade 2, then $\downarrow 1$ dose level
HEPATIC	
Alkaline phosphatase and/or Gamma-glutamyl transpeptidase (GGT)	
Isolated elevations of any grade	Maintain dose level
Total Bilirubin** (for patients with Gilbert Syndrome these dose modifications apply to changes in direct [conjugated] bilirubin only)	
Grade 1 ($> ULN$ and $\leq 1.5 \times ULN$)	Maintain dose level with liver function test (LFTs)*** monitored as per protocol
Grade 2 (> 1.5 and $\leq 3.0 \times ULN$) with ALT or AST $\leq 3.0 \times ULN$	Omit dose until resolved to \leq Grade 1, then: If resolved in ≤ 7 days, then maintain dose level If resolved in > 7 days, then $\downarrow 1$ dose level
Grade 3 (> 3.0 and $\leq 10.0 \times ULN$) with ALT or AST $\leq 3.0 \times ULN$	Omit dose until resolved to \leq Grade 1, then: If resolved in ≤ 7 days, $\downarrow 1$ dose level If resolved in > 7 days discontinue patient from LDK378

Worst toxicity (CTCAE 4.03 Grade)*		Dose Modifications for LDK378
Grade 4 ($> 10.0 \times \text{ULN}$)		Permanently discontinue patient from LDK378
AST or ALT		
Grade 1 ($> \text{ULN}$ and $\leq 3.0 \times \text{ULN}$)		Maintain dose level with LFTs*** monitored per protocol
Grade 2 (> 3.0 and $\leq 5.0 \times \text{ULN}$) without total bilirubin elevation to $> 2 \times \text{ULN}$		Maintain dose level with LFTs*** monitored per protocol
Grade 3 (> 5.0 and $\leq 20.0 \times \text{ULN}$) without total bilirubin elevation to $> 2 \times \text{ULN}$		Omit dose until resolved to \leq Grade 1, then $\downarrow 1$ dose level
Grade 4 ($> 20.0 \times \text{ULN}$) without total bilirubin elevation to $> 2.0 \times \text{ULN}$		Omit dose until resolved to \leq Grade 1, then $\downarrow 1$ dose level
AST or ALT and concurrent Total bilirubin		
AST or ALT $> 3.0 \times \text{ULN}$ with total bilirubin $> 2.0 \times \text{ULN}$ in the absence of cholestasis or hemolysis		Permanently discontinue patient from LDK378 Refer to Section 6.2.4.2 for additional follow-up
PANCREATIC		
Amylase and/or lipase elevations (in the absence of clinical symptoms)		
Grade 1 ($> \text{ULN}$ and $\leq 1.5 \times \text{ULN}$)		Maintain dose level
Grade 2 ($> 1.5 - 2.0 \times \text{ULN}$)		Maintain dose level
Grade ≥ 3 ($> 2.0 \times \text{ULN}$)		Omit dose until resolved to \leq Grade 1, then $\downarrow 1$ dose level
Note: Withhold ceritinib for acute onset of new or progressive unexplained abdominal symptoms, such as severe pain or vomiting; perform diagnostic procedures (e.g., abdominal CT scan or ultrasound) to exclude pancreatic pathology.		
RENAL		
Serum creatinine		
Grade 1 (> 1 and $\leq 1.5 \times \text{baseline}$; $> \text{ULN}$ and $\leq 1.5 \times \text{ULN}$)		Maintain dose level
Grade 2 (> 1.5 and $\leq 3.0 \times \text{baseline}$; > 1.5 and $\leq 3.0 \times \text{ULN}$)		Omit dose until resolved to \leq Grade 1, then: If resolved in ≤ 7 days, then maintain dose level If resolved in > 7 days, then $\downarrow 1$ dose level
Grade 3 ($> 3.0 \times \text{baseline}$; > 3.0 and $\leq 6.0 \times \text{ULN}$)		Omit dose until resolved to \leq Grade 1, then $\downarrow 1$ dose level
Grade 4 ($> 6.0 \times \text{ULN}$)		Permanently discontinue patient from LDK378

Worst toxicity (CTCAE 4.03 Grade)*		Dose Modifications for LDK378		
GASTROINTESTINAL				
Diarrhea****				
Grade 1	Maintain dose level but adjust anti-diarrhea treatment			
Grade 2 (despite maximal anti-diarrheal medication)	Omit dose until resolved to ≤ Grade 1, then maintain dose level. If diarrhea returns as ≥ Grade 2, then omit dose until resolved to ≤ Grade 1, then ↓ 1 dose level			
Grade 3 (despite maximal anti-diarrheal medication)	Omit dose until resolved to ≤ Grade 1, then ↓ 1 dose level			
Grade 4 (despite maximal anti-diarrheal medication)	Omit dose until resolved to ≤ Grade 1, then ↓ 1 dose level			
Nausea*****				
Grade 1 or 2	Maintain dose level but adjust anti-emetic treatment			
Grade 3 (despite standard anti-emetics)	Omit dose until resolved to ≤ Grade 1, then ↓ 1 dose level			
Vomiting*****				
Grade 1	Maintain dose level but adjust anti-emetic treatment			
Grade 2 (despite standard anti-emetics)	Omit dose until resolved to ≤ Grade 1, then maintain dose level. If vomiting returns as ≥ Grade 2, then suspend dose until resolved to ≤ Grade 1, then ↓ 1 dose level.			
Grade 3 (despite standard anti-emetics)	Omit dose until resolved to ≤ Grade 1, then ↓ 1 dose level			
Grade 4 (despite standard anti-emetics)	Omit dose until resolved to ≤ Grade 1, then ↓ 1 dose level			
METABOLIC				
Any Grade hypophosphatemia	Treatment with phosphate supplements as clinically indicated and maintain dose level			
Persistent hyperglycemia (glucose > 250 mg/dL) despite optimal anti-hyperglycemic therapy	Omit dose until hyperglycemia is adequately controlled, then resume LDK378 at ↓ 1 dose level If adequate hyperglycemic control cannot be achieved with optimal medical management, permanently discontinue patient from LDK378.			
GENERAL DISORDERS				
Fatigue (asthenia)				
Grade 1 or 2	Maintain dose level			
Grade 3	If grade 3 fatigue resolves to Grade 2 in ≤ 7 days, maintain dose level If grade 3 fatigue lasts > 7 days, omit dose until resolved to ≤ Grade 2 and then ↓ dose level			

Worst toxicity (CTCAE 4.03 Grade)*	Dose Modifications for LDK378
PULMONARY	
Notes:	

 Withhold LDK378 for acute onset of new or progressive unexplained pulmonary symptoms, such as dyspnea, cough and fever and during diagnostic workup for pneumonitis/ILD. During evaluation of potential grade 2, 3, and 4 pneumonitis, if an infectious etiology is confirmed (i.e., pneumonia) and pneumonitis is excluded, then consider resuming LDK378 at current dose level after the pneumonia resolves. 	
PNEUMONITIS	
Any Grade treatment-related ILD/pneumonitis	Permanently discontinue patient from LDK378
CARDIAC	
Electrocardiogram QT corrected (QTc) interval prolonged	
Grade 1 (QTc 450-480 ms) Grade 2 (QTc 481-500 ms)	Maintain dose level
Grade 3 (QTc \geq 501 ms on at least two separate ECGs)	
Omit dose until QTc is less than 481 ms, then \downarrow 1 dose level.
 
- Assess the quality of the ECG recording and the QT value and repeat if needed.
 
Repeat ECG in 24 hours, or less, as clinically indicated; continue monitoring as clinically indicated until QTc $<$ 481 ms
 
In addition:
 
 - Determine the serum electrolyte levels (in particular hypokalemia, hypomagnesemia). If abnormal, correct abnormalities before resuming study drug treatment - Review concomitant medication use for drugs with the potential to increase the risk of drug exposure related to QT prolongation - Consider collecting a time-matched PK sample and record time and date of last study drug intake 
After resumption of dosing:
 
-Repeat ECGs 7 days after dose resumption for all patients who had therapy interrupted due to QTc \geq 501 ms.

Grade 4 (QTc \geq 501 or $>$ 60 ms change from baseline and Torsades de pointes or polymorphic ventricular tachycardia or signs/symptoms of serious arrhythmia)	Permanently discontinue patient from LDK378

Worst toxicity (CTCAE 4.03 Grade)*	Dose Modifications for LDK378
Bradycardia	
Grade 1 or 2	Omit dose until recovery to asymptomatic bradycardia or to a heart rate ≥ 60 bpm Evaluate concomitant medications known to cause bradycardia, and adjust the dose of LDK378.
Grade 3 Grade 4 (in patients taking a concomitant medication also known to cause bradycardia or a medication known to cause hypotension)	Omit dose until recovery to asymptomatic bradycardia or to a heart rate ≥ 60 bpm If the concomitant medication can be adjusted or discontinued, resume LDK378 at $\downarrow 1$ dose level with frequent monitoring
Grade 4 (in patients who are not taking a concomitant medication also known to cause bradycardia or known to cause hypotension)	Permanently discontinue LDK378.

* Common Terminology Criteria for Adverse Events (CTCAE) version 4.03. All dose modifications should be based on the worst preceding toxicity.
 ** If Grade 3 or 4 hyperbilirubinemia is due to the indirect (non-conjugated) component only, and hemolysis as the etiology has been ruled out as per institutional guidelines (e.g., review of peripheral blood smear and haptoglobin determination), then $\downarrow 1$ dose level and continue treatment at the discretion of the Investigator.
 ***LFTs include albumin, ALT, AST, total bilirubin, alkaline phosphatase and GGT
 **** Dose modifications apply to patients who experience diarrhea despite appropriate antidiarrheal medication. This medication should be started at the first sign of abdominal cramping, loose stools or overt diarrhea (see [Section 6.3.2.5](#))
 ***** Dose modifications apply to patients who experience nausea and/or vomiting despite appropriate antiemetic medication. This medication should be started at the first sign of nausea and/or vomiting (see [Section 6.3.2.6](#))

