- Bradycardia: asymptomatic cases of bradycardia have been observed in patients treated with ceritinib in clinical studies. Repeated ECG tracings will be performed throughout the study to closely monitor cardiovascular safety. Risk will also be minimized by monitoring concomitant use of other agents known to cause bradycardia (e.g., beta-blockers, non-dihydropyridine calcium channel blockers, clonidine, and digoxin) to the extent possible. Heart rate and blood pressure will also be monitored regularly during the study.
- Hyperglycemia: events of hyperglycemia (all grades) have been reported in less than 10% of patients treated with ceritinib in clinical studies; 5% of patients reported a grade 3/4

event. The risk of hyperglycemia was higher in patients with diabetes mellitus and/or concurrent steroid use. Patients will be closely monitored throughout the study for any signs and symptoms related to elevated blood glucose levels. Risk will be minimized by including subjects with fasting plasma glucose levels ≤ 200 mg/dL (≤ 11.1 mmol/L) at screening (see inclusion #7).

- Gastrointestinal toxicity: diarrhea, nausea, and vomiting have been very commonly reported; 12.2% of patients reported a grade 3/4 event of diarrhea, nausea, or vomiting. Risk to patients will be minimized during the study by closely monitoring symptoms and managing patients using standards of care, including anti-diarrheals, anti-emetics, or fluid replacement, as indicated.
- Pancreatitis (including lipase and amylase elevations): in most cases, pancreatic enzyme elevations have been mild to moderate, and have typically reversed with interruption of ceritinib. Few patients have experienced pancreatitis with severe upper abdominal pain. Patients will be monitored closely for any related signs and symptoms. In order to minimize the risk to patients during the study, patients with a history of pancreatitis or a history of increased lipase or amylase levels that was due to pancreatic disease will be excluded. In addition, serum amylase must be $\leq 2 \times$ ULN and serum lipase must be within normal limits at screening.

Conclusion

The outstanding anti-tumor activity and resulting clinical benefit combined with the manageable safety profile of ceritinib strongly support a positive benefit-risk balance for ALK-positive NSCLC patients, regardless of whether the patients had received prior ALK inhibitor treatment or not.

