6.2 Dose modifications

6.2.1 Dose modification and dose delay

For patients who do not tolerate the protocol-specified dosing schedule, dose adjustments are permitted in order to allow the patient to continue the study treatment. Any changes in LDK378 administration must be recorded on the Dosage Administration Record eCRF.

General guidelines for dose modifications for toxicities other than those listed in Table 6-3.

For grade 1 and tolerable grade 2 treatment-related toxicities, patients may continue at the current dose of study treatment. For intolerable grade 2 treatment-related toxicities, dosing should be interrupted until resolution to grade 1 or lower followed by dose reduction to the next dose level.

For grade 3 or grade 4 treatment-related toxicity that is not considered by the investigator to be life-threatening, patients should interrupt study treatment until resolution to grade 1 or lower; then study treatment may continue following a dose reduction to the next dose level, if, in the opinion of the Investigator, the patient continues to experience clinical benefit. For any grade 3 or 4 treatment-related toxicity that is considered by the investigator to be life-threatening, permanently discontinue study treatment.

More detailed LDK378 dose modification guidelines are described in [Section 6.2.3.](#) for selected toxicities. Any planned variance from these guidelines in view of patient safety must first be discussed with the sponsor unless there is an urgent need for action.

All dose modifications, interruptions or discontinuations must be based on the worst preceding toxicity as graded by the NCI Clinical Toxicity Criteria (NCI-CTCAE version 4.03).

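### In Table 6-3 an asymptomatic patient with grade 1 or 2 bradycardia meets the hold and its release at the same moment, and the dose adjustment that follows is undefined

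*Protocol*

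**What the plan says.** The bradycardia part of Table 6-3 (protocol Section 6.2.3) opens with a row for grade 1 or 2. It prints no heart-rate limits for the grades and no condition on symptoms. The action is "Omit dose until recovery to asymptomatic bradycardia" or until the heart rate is at least 60 bpm. The row continues: "Evaluate concomitant medications known to cause bradycardia, and adjust the dose of LDK378".

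The next row covers grade 3, and grade 4 in patients on a contributing concomitant drug. It repeats the release wording and then states a dose for one situation: "If the concomitant medication can be adjusted or discontinued, resume LDK378 at" one level lower.

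Section 1.3 shows that silent cases are expected: "asymptomatic cases of bradycardia have been observed in patients treated with ceritinib in clinical studies".

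Three other provisions bear on the point:

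- Section 6.2.3 sends every reduction down the Table 6-2 ladder (750, 600, 450, 300 mg), forbids going back up, and allows three modifications before treatment must stop.
- Protocol Section 10.5.3.5 summarises tolerability, part of a primary objective, by reductions and interruptions due to adverse events.
- SAP Section 3.2.9.1 names bradycardia as an event of special interest and tabulates such events by whether they required dose adjustment or interruption.

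**The concern.** A hold rule needs an entry condition and an exit condition that cannot both be true at the start. Here they can, for a kind of case the protocol itself describes. The scheduled triplicate ECGs (Tables 7-4 and 7-5) and pulse measurements (Section 7.2.2.2) make it likely that such cases are found.

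The second instruction in the row adds to the difficulty. Nearly every other row that holds the dose ends in a defined step: keep the level, go down one, or stop. This row says only that the dose is to be adjusted.

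Two things are at stake. For the patient, a reduction made on one reading is permanent and uses up one of three modifications, while another reading leaves the level unchanged. For the analysis, the counts of bradycardia requiring interruption or adjustment, and the times to first reduction and first interruption (SAP Section 3.2.5), would partly reflect how each site read the row.

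**Working it through.** The plan states no figure to reproduce. The check is a logical one, followed by a search for text that settles it and a rough bound on size.

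**Step 1: entry against release.** Entry is bradycardia graded 1 or 2. Release is (asymptomatic) OR (heart rate 60 bpm or more). The dose is held while entry is true and release is false.

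- Symptomatic, below 60 bpm: entry true; release = false OR false = false. The dose is held and the rule is coherent.
- Asymptomatic, below 60 bpm: entry true; release = true OR false = true. The hold has zero length.

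Taken literally, the heart-rate limb adds something only for a patient with symptoms. A site may reason that a patient without symptoms has nothing to recover from on the first limb, and so apply the second. It would then hold until 60 bpm. The same patient is held for no days or for some days.

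**Step 2: the adjustment.** The second sentence of the row carries no condition, so it applies whether or not there was a hold. It gives neither direction nor size. One Table 6-2 step is 150 mg, which is 150/750 = 20% of the starting dose.

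**Step 3: does other text settle it?**

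- Section 6.2.1 introduces its rules as "General guidelines for dose modifications for toxicities other than those listed in Table 6-3". Bradycardia is listed there, so they do not apply.
- Section 6.2.2 allows resumption at the same dose after toxicities not described in Table 6-3, which again leaves bradycardia out.
- Section 6.2.3 fixes the ladder once a reduction is made. It does not say whether this row requires one.
- The heart-rate and pulse limits in SAP Sections 3.2.9.3 and 3.2.9.4 are reporting thresholds and do not direct dosing.

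**Step 4: how it reaches the tables.** Under SAP Section 4.1.6 a 0 mg dose on one or more days is an interruption, so a hold to 60 bpm is counted and a void hold is not. Under protocol Section 8.1.1 an abnormal test result is an adverse event if, among other grounds, it requires a change in study medication. For a silent case not otherwise judged significant, the reading of this row can therefore also decide whether an event is recorded.

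**Step 5: size.** Table 1-1 lists adverse events seen in at least 10% of 255 patients at 750 mg in the earlier global study. No bradycardia term appears, so each such term was reported in fewer than 25.5, that is at most 25, patients. If the rate here were similar, 0.10 x 103 = 10.3, or about 10 patients per term at most. At Amendment 3, 103 - 66 = 37 patients were still on treatment, and 0.10 x 37 = 3.7. These are loose guides. Silent cases may not have been reported as events, the SAP groups several preferred terms under one special-interest category, and the asymptomatic grade 1 or 2 share is not given.

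**The case against.** The strongest reply is that this is loose wording with a natural meaning. Recovery to an asymptomatic state presupposes symptoms, so a patient without them is simply not held. That is a fair reading of the hold, but the row does not state it, and it leaves the undefined adjustment in place.

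A reader might infer that an asymptomatic patient could properly receive no action at all. The documents do not support that as a literal reading. The instruction to review concomitant drugs and adjust the dose is unconditional, so only the hold falls away. No action follows only if the whole row is taken as limited to symptomatic patients, a limit the row does not print.

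A reader might also take Section 1.3 to mean that all cases on this drug were asymptomatic. It says only that such cases have been seen.

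Three further points on the other side stand in part:

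- Any downward adjustment must be a Table 6-2 step, because Section 6.2.3 governs every reduction. What stays open is whether a reduction is required and by how many steps. The fatigue row also omits the number of levels, though it does give the direction.
- The study has one arm and no formal test (protocol Section 10.10), so no treatment comparison is biased.
- Slow heart rates are also reported without regard to dose action. However, the notable-value counts need a heart rate below 50 bpm or a pulse of 50 bpm or less, so a patient at 55 bpm would appear in neither.

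**Conclusion.** The point holds as a defect in one row. The grade 1 or 2 bradycardia rule defeats its own hold for an asymptomatic patient below 60 bpm, and its dose adjustment lacks direction and size. Patients with the same event could be held or not, reduced or not, and counted accordingly in the tolerability summary.

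The textual conflict is certain; its numerical weight is not. The documents give no incidence of asymptomatic grade 1 or 2 bradycardia, so no count of affected patients should be quoted as an estimate. What can be said is that no single bradycardia term reached 10% in Table 1-1, and that a change made at Amendment 3 could have reached at most 37 patients. The effect on the study's descriptive results is probably small. The point is still worth correcting because a reduction cannot be reversed and tolerability is part of a primary objective. The verdict assumes that the grades, whose limits the row does not print, admit asymptomatic patients, as the unrestricted trigger and Section 1.3 suggest.

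**What to change.** Reconcile three elements of the grade 1 or 2 row: the trigger, the release condition and the adjustment. An asymptomatic patient should fall under one instruction only, and the adjustment should be expressed in the terms of Tables 6-3 and 6-2. Check the same release wording in the grade 3 and 4 row at the same time. Which rule is adopted is for the sponsor's clinical team.

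The cost is one or two table rows in an amendment or clarification letter; Amendment 3 had already opened Table 6-3. The change cannot help patients already off treatment. For them, the action taken with study drug is already recorded for each adverse event (protocol Section 8.1.1), so the report can show how sites handled the recorded bradycardia events without new data collection.

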6.2.4 Follow-up for toxicities

An unscheduled visit should be performed in all cases below where toxicity monitoring is recommended more frequently than defined by the schedule of assessments ([Table 7-1](#)).

